9.3. Exploratory Efficacy Analyses

In addition, for exploratory analysis, ANOVA (or ANCOVA with baseline measure as covariate) will be applied to test for treatment difference at each separate week. Other univariate and multivariate models could be explored, if warranted.

10. SAFETY ANALYSES

The safety analysis will be performed based on the Safety Population. Safety variables include AEs, clinical laboratory parameters, vital signs, physical examinations, and ECG.

10.1. Adverse Events

Safety summaries will include the incidence of treatment-emergent adverse events (TEAEs), which are defined as any event that began on or after the date of the first treatment dose or worsened in severity or frequency after treatment dose was initiated. Events worsening in severity will be considered new AEs. AEs recorded on the CRF that began prior to treatment and did not worsen in severity will be recorded as medical history will not be included in the AE summary tables and data listings. Any AEs happens in long-term safety follow-up will be reported in a separate listings and not included in the main planned analyses.

All TEAEs will be coded using version 17.1 of Medical Dictionary for Regulatory Activities (MedDRA) and summaries will present data by System Organ Class (SOC) and preferred term (PT).

The following conventions will be followed in summarizing multiple occurrences of an adverse event for a certain assessment period when summarizing data from individual participant:

- Each subject will be counted only once within a body system (SOC) or a preferred term;
- The highest known severity within a body system or a preferred term will be assigned to the event;
- The strongest relationship within a body system or a preferred term will be assigned to the event.

The denominator used for calculation of the percentages will be the number of subjects in the Safety population per treatment.

Specifically, TEAEs will be summarized in the Safety Population. An overall summary of TEAEs, including number of subjects in population, number of subjects with one or more TEAEs, number of participants with one or more Serious TEAEs, number of deaths (if any), and number of subjects experiencing AEs resulting in discontinuation, will be presented in Table 14.3.1.1 by treatment group. The frequency and percentage of AEs by SOC and PT for each treatment group will be presented in Table 14.3.1.2.

The frequency and percentage of AEs related to study drug (Possibly Related, Probably Related, and Definitely Related) by treatment group will be displayed by treatment in Table 14.3.2.

A listing of all AE data sorted by subject, including the verbatim term, MedDRA SOC and preferred term, and all other information from the AE CRF will be displayed in Listing 16.2.7.1. This listing will include a field for Study Day calculated as [(AE start date, minus date of first dose of study medication) +1]. Similarly, individual AE records of SAEs will be listed in

Listing 16.2.7.2. Any deaths occurring on study will be displayed in Listing 16.2.7.3. AEs that lead to discontinuation will be listed in Listing 16.2.7.4.

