4.3 Exclusion criteria

1. A woman with a positive serum (HCG) pregnancy test or lactating. (All women of child bearing years who have not had a hysterectomy will have a serum HCG.)
2. History of three or more culture documented recurrent urinary tract infections per year.
3. Current history of bladder outlet obstruction secondary to urethral stenosis, third degree cystocele, or obstruction from prior urethral sling surgery documented by cystoscopy, urothelial cancer, or other significant genitourinary disorders except incontinence (previous vesicle lithiasis or bladder stones that have been successfully removed are not an exclusion).
4. Current history or previous diagnosis of painful bladder syndrome (interstitial cystitis) with pain in the region of the pelvis, perineum, or lower abdomen relieved by voiding.
5. A urine culture (≥ 1000 colonies/ml) of a urinary pathogen from a catheterized urine obtained at screening.
6. Current history of neurological bladder dysfunction.
7. A life expectancy of less than 12 months.
8. Current history of Grade 2 or greater cystocele.

9. Stress urinary incontinence as determined by observation of the participant coughing while standing with a full bladder and/or response of 2 or 3 on the following Stress Urinary Incontinence question:

Do you experience leakage when laughing, coughing, lifting heavy objects or other types of discreet, moderately intense activities?

0= NONE: No leakage

1= MILD: Minimal leakage on rare occasions during these types of activities; easily tolerated; do not use pads for this.

2=MODERATE: Enough leakage that it requires occasional use of pads and may interfere with usual activity & tasks

3 =SEVERE: Extreme leakage & discomfort that stops all activity &/tasks and requires use of pads on all occasions

10. An indwelling urethral catheter or need for clean intermittent self-catheterization.
11. Any screening laboratory values outside of the normal laboratory range, as defined by the laboratory normal ranges and in the judgment of the investigator is considered clinically significant (hepatic biochemical markers \leq twice the upper limit of the normal reference range may be accepted with written consent of sponsor).
12. A hemoglobin A1c $>7\%$ in a person with diabetes.
13. A history of sickle-cell disease, sickle cell trait, or any other medical condition that, in the judgment of the investigator, would produce significant risk to the patient.

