9.1 Adverse Events Definitions and Monitoring

9.2 Adverse Event

An adverse event is any unfavorable and unintended diagnosis, symptom, sign (including an abnormal laboratory finding), syndrome or disease which either occurs during the study, having been absent at baseline, or, if present at baseline, appears to worsen.

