3. STUDY OBJECTIVES

3.1. Primary Objectives

The primary objective of this study is to evaluate the occurrence of treatment emergent adverse events (TEAEs) and their relationship to a single treatment of approximately 20 to 30 bladder wall intramuscular injections of *h*Maxi-K compared to placebo (PBS-20% sucrose). Two dose levels (16,000 µg and 24,000 µg) in females with moderate OAB/DO of ≥ six months duration are planned. In each dose level, 6 participants will receive *h*Maxi-K and 3 will receive placebo.

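### SAP 10.1 counts a pre-existing event that worsens only in frequency as treatment-emergent, and also excludes it from the AE tables and listings

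*SAP*

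**What the plan says.** SAP 3.1 makes TEAEs the main subject of the trial: "The primary objective of this study is to evaluate the occurrence of treatment emergent adverse events (TEAEs) and their relationship to a single treatment".

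The opening paragraph of SAP 10.1 then gives three consecutive rules.

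1. **Definition.** A TEAE is "any event that began on or after the date of the first treatment dose or worsened in severity or frequency after treatment dose was initiated".
2. **New-event rule.** "Events worsening in severity will be considered new AEs".
3. **Exclusion.** "AEs recorded on the CRF that began prior to treatment and did not worsen in severity will be recorded as medical history"; these events "will not be included in the AE summary tables and data listings". The sentence is grammatically broken where the two parts join, but its effect is clear.

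Protocol 9.2 defines an adverse event more broadly than rule 3. A condition counts when, "if present at baseline, appears to worsen", with no restriction to severity. SAP 14 declares no changes from the protocol's statistical methods.

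**The concern.** Rule 1 has two routes for a pre-existing condition to become treatment-emergent: greater severity or greater frequency. Rules 2 and 3 recognise only severity. An event that takes the frequency route is a TEAE by definition and is excluded by the sentence that decides what reaches the tables. Nothing elsewhere in the SAP says which rule prevails, so the choice falls to whoever programs the AE dataset.

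If rule 3 is applied, the reported TEAE count can stay the same or fall, but cannot rise. This bears on the primary objective, in groups small enough for one participant to be visible in a percentage.

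**Working it through.** The plan states no figure on this point, so there is none to reproduce. The check is to run the rules over every possible case.

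**Step 1: all combinations.** An event has onset before or after dosing, severity worse or not, and frequency worse or not, which gives 2 × 2 × 2 = 8 cases. Rule 1 makes it a TEAE if onset is post-dose, or severity is worse, or frequency is worse. Rule 3 excludes it if onset is pre-dose and severity is not worse.

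| Onset | Severity worse | Frequency worse | Rule 1 | Rule 3 |
|---|---|---|---|---|
| Pre | No | No | not a TEAE | excluded |
| Pre | No | Yes | **TEAE** | **excluded** |
| Pre | Yes | No | TEAE | kept |
| Pre | Yes | Yes | TEAE | kept |
| Post | No | No | TEAE | kept |
| Post | No | Yes | TEAE | kept |
| Post | Yes | No | TEAE | kept |
| Post | Yes | Yes | TEAE | kept |

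Exactly 1 of the 8 cases conflicts: pre-dose onset, severity unchanged, frequency worse. With frequency added to rule 3, the number of conflicts is 0 of 8.

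**Step 2: can the conflicting case occur?**

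- Protocol 9.6 asks for all AEs on the E-CRF, including those in the screening period where applicable, and Protocol Table 1 schedules AE assessment at Visit 1A. Catheterisation and cystometry precede dosing (Protocol 7.2 and 7.3), so urinary symptoms may already be on record.
- For events outside the toxicity table, Protocol 9.5 grades by intensity of symptoms, limitation of daily activities or level of abnormality. More frequent episodes need not raise the grade. In Appendix A the hypertension row does build recurrence into the grade, so that event would be caught by severity.

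**Step 3: size for one participant.** SAP 3.1 plans 6 active and 3 placebo participants per dose level, hence 12 pooled active and 6 pooled placebo. SAP 10.1 counts each subject once per category over the Safety Population. If the dropped event is her only one in that category, the change is 1/n:

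- one dose group, or pooled placebo: 1/6 = 16.7 percentage points;
- pooled active: 1/12 = 8.3 percentage points.

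**Step 4: chance of any such case (assumed rates only).** The documents give no rate of frequency-only worsening. If each of 18 participants had an independent probability q of one, the chance of at least one is 1 − (1 − q)^18: 60% for q = 5%, 85% for q = 10% and 98% for q = 20%. These illustrate scale and are not estimates for this trial.

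**The case against.** The strongest reply is that the affected class is narrow and that the protocol's recording rules shrink it further.

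- **Recording on the AE log.** Protocol 7.4 sends new events or changes reported after dosing to the Adverse Event log. A frequency increase is such a change. If it is entered with a post-dose start date, rule 3 does not touch it. This stands as mitigation, but neither document requires that date convention, and the SAP creates a new AE only for worsening severity.
- **Urinary tract infection.** A reader might infer that recurrent infections would be the main loss, because Protocol 4.3 excludes only a "History of three or more culture documented recurrent urinary tract infections per year", and infections recurred in the earlier OAB trial. The documents do not support this. A post-dose infection is ordinarily a discrete event with its own onset date, so it is a TEAE under the first limb of rule 1. A pathogen in the screening culture is exclusionary (Protocol 4.3) unless treated and cleared (Protocol 7.2), and a dipstick precedes dosing (Protocol 7.4). Nor do the documents say that bladder injection would raise the frequency of infection rather than its grade; Protocol 7.4 provides prophylactic antibiotics.
- **Recoverability.** A reader might also infer that an excluded event disappears from the study report. That goes too far. Medical history is listed by subject in Listing 16.2.4.2 (SAP 8.3), and SAP 10.1 itself describes Listing 16.2.7.1 as covering all AE data, which sits awkwardly with rule 3. What remains is that a medical-history entry would show a baseline condition and not its worsening after dosing.

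None of these points reconciles the two sentences.

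**Conclusion.** The concern holds as an internal inconsistency in the rules behind the primary safety endpoint. It is confined to one type of event: a condition carried as a continuous pre-dose record that becomes more frequent after dosing at an unchanged grade. New-onset events and severity worsening are handled consistently.

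The shifts of 16.7 and 8.3 points assume the planned group sizes, that rule 3 is the one applied, and that the participant has no other event in the category concerned. For overall TEAE incidence this means no other TEAE at all. They should not be read as an expected bias. Nor does the wording favour either arm, since rule 3 applies to active and placebo participants alike.

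**What to change.** Before unblinding, make two wording changes in SAP 10.1:

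1. In the exclusion sentence, add *or frequency* after *severity*, so that only pre-treatment events that worsened in neither respect go to medical history. This change alone removes the contradiction.
2. In the new-event sentence, make the same addition, so that a frequency increase is counted as a new AE after dosing instead of depending on how the site dated it.

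Both bring the section into line with its own TEAE definition and with Protocol 9.2.

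Optionally, keep every AE record in Listing 16.2.7.1 with a TEAE yes/no flag. This also settles the tension between the exclusion and the stated scope of that listing.

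The cost is two short edits and, if adopted, one listing flag. Sample size, power and data collection do not change. The reported TEAE rate may be slightly higher.

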10.2. Clinical Laboratory Evaluations

Clinically significant abnormal laboratory values will be reported as AEs and the grade will be assessed according to Protocol Appendix A and will be reported in the AE analyses.

Summary statistics of numerical laboratory test results (mean, standard deviation, median, min and max) of test results and changes of test results from screening (V1) and V2 predose for laboratory tests (the last evaluation prior to treatment) will be reported for hematology and clinical chemistry at each scheduled time point. Specifically, information of pooled *hMaxi-K* and placebo will be displayed in Table 14.3.4.1 for hematology and Table 14.3.4.2 for clinical chemistry.

Individual test result records, including repeat assessments, and comments for hematology, clinical chemistry, urinalysis and other miscellaneous tests will be displayed in Listings 16.2.8.4.1, 16.2.8.4.2, 16.2.8.5.1, 16.2.8.5.2, 16.2.8.6.1, 16.2.8.6.2. The urine culture per participant results will be displayed in Listing 16.2.8.7.

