Statistical Analysis	Both the safety data and data to assess activity will be analyzed using summary descriptive statistics for the four cohorts and the total study population. The group sample sizes of 6 per arm achieve 80% power to detect a 30% reduction in frequency of voiding to placebo assuming a standard deviation of 2.5 with a significance level of 0.05 using a two-sided, two sample t-test. A comparison to baseline will also be done using a two-sided t- test. Total number of active treatment participants (N=12) will also be compared to total number of placebo participants (N=6).

Table 1. Procedures By Visit

Phase	Screening Phase			Post-Treatment Follow up Visits						
	Visit 1	Visit 1A ⁿ	Visit 2	Telephone Follow-up ^j	Visit 3	Visit 4	Visit 5	Visit 6	Visit 7	Visit 8
Day	-14	-14 to -8	0 (Baseline)	Day 1 & 3	8	15	29	57	85	169 (Final)
Week	-2		0	0	1	2	4	8	12	24
Visit Window (days)		+2	+2	Day 3±1	+2	+2	±2	±3	±5	±5
Signed Informed Consent	▲									
Evaluation of Inclusion /Exclusion Criteria	▲	▲	▲ ^f							
Demographics and Medical/ Surgical History	▲									
Physical Examination	▲		▲ ^f		▲	▲	▲	▲	▲	▲
ECG	▲		▲ ^a		▲		▲			▲
Previous / Concomitant Medication Assessment	▲	▲	▲ ^f		▲	▲	▲	▲	▲	▲
Vital Signs ^b	▲		▲ ^{f,l}		▲	▲	▲	▲	▲	▲
Objective OAB /DO Evaluation (Cystometry) ^b		▲ ^d					▲			▲
Bladder scan ^c	▲					▲		▲		▲
Dispense Daily Voiding Diary/Urgency questionnaire ⁱ	▲	▲	▲ ^f		▲	▲	▲	▲	▲	
Pad Test ^m		▲	▲		▲	▲	▲	▲	▲	▲
QoL (King’s Health Questionnaire) and SF-12			▲ ^f				▲	▲	▲	▲
Subjective Evaluation of Disease State ^k			▲ ^f		▲	▲	▲	▲	▲	▲
Subjective Evaluation of Response to Treatment ^k					▲	▲	▲	▲	▲	▲
ICIQ-SF			▲ ^f				▲	▲	▲	▲
Urinalysis and Urine Cultures ^d	▲	▲	▲ ^f		▲	▲	▲		▲	▲
Hematology Laboratory Tests ^e	▲		▲		▲	▲	▲		▲	▲
Chemistry Laboratory Tests ^e	▲				▲	▲	▲		▲	▲
Pharmacokinetic Assessment (urine and blood hSlo cDNA)			▲ ^{f,g}		▲	▲	▲	▲	▲	▲ ^g
Adverse Event Assessment		▲	▲ ^f	▲ ^j	▲	▲	▲	▲	▲	▲
Study Drug administered			▲							

- a. ECG will be done prior to administration of study drug and at 2 hours post dosing.

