10.4 Analysis of Endpoints

The methods described in this section will be updated during the course of the study. The final version of the statistical analysis plan (SAP) will be issued before the treatment code is broken.

This double blind, phase 1 study is designed to evaluate the safety of a single bladder injections of 2 different doses of *hMaxi-K* in individual participants. Both the safety data and data to assess efficacy will be analyzed using summary descriptive statistics for the two cohorts and the total study population. Associations between study therapy and the outcomes will be assessed using-repeated measures analyses, and explored in multivariate models, as needed.

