
Objectives:
 
Primary: The primary objective of this study is to evaluate occurrence of Adverse Events and their relationship to hMaxi-K following multiple intramuscular (IM) injections into the bladder wall. Two dose levels (16,000 µg and 24,000 µg by IM injection into the bladder wall) in females with moderate OAB/DO of ≥ six months duration are initially planned.
 
 • Treatment Emergent Adverse Events (TEAEs) – frequency and percentage of TEAEs, TEAEs by maximum severity and by relationship to study drug by treatment; summary of any AEs resulting in discontinuation of administration of study drug, serious adverse events (SAEs), and deaths during the study • Secondary: The secondary objectives of this study are to evaluate the following safety parameters: 
 – Clinical laboratory tests - changes and shift (whether the tests are within clinical normal range, whether they are clinically significant) from baseline by treatment – Electrocardiogram – change and shift from baseline (per ECG over-reader) by treatment – Vital Signs (systolic and diastolic blood pressure, and pulse rate) - change and shift from baseline 
The last assessment made prior to dosing of double-blind study drug will be used as the baseline for all analyses of these safety parameters.
 
In addition, efficacy parameters will be evaluated as change from baseline compared to placebo. Comparisons will be made between combined placebo (N = 6) vs. 16,000 µg (N = 6) and 24,000 µg (N = 6) active hMaxi-K group separately, and also between combined placebo and combined active group (N = 12), as well as between treatment comparisons for a dose response analysis. Efficacy evaluations will include the number of micturitions per day, volume per micturition, urgency episodes (1 or greater on urgency scale), and incontinence episodes from voiding diary, and pad weight. Efficacy evaluations will also include the following cystometric evaluations performed by the overreader at week 4 and 24: 1) Detrusor overactivity ≥ 5 cm H₂O (yes/no- INCLUSION CRITERIA); 2) Volume at first desire to void; 3) Detrusor pressure at beginning of voiding (prior to onset of first contraction, either volitional or involuntary); 4) Volume at first involuntary contraction; if detrusor overactivity (DO) present-Not applicable if no DO present; 5) Maximum detrusor pressure at FIRST contraction.
	

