Efficacy evaluations will include the number of micturitions per day, volume per micturition, urgency episodes and incontinence (or accident) episodes from voiding diary, and pad weight. Efficacy evaluations will also include the following cystometric evaluations performed by the site and/or the overreader at week 4 and 24: 1) Detrusor overactivity ≥ 5 cm H₂O (yes/no- INCLUSIONCRITERIA); 2) Volume at first desire to void; 3) Detrusor pressure at beginning of voiding (prior to onset of first contraction, either volitional or involuntary); 4) Volume at first involuntary contraction; if detrusor overactivity (DO) present-Not applicable if no DO present; 5) Maximum detrusor pressure at FIRST contraction.

PVR on bladder scan, and general and bladder specific quality of life assessments measured by participant evaluation using Kings Health Care Questionnaire (KHQ) and participant evaluation of response to treatment will also be evaluated.

Statistical methods:

Both the safety data and data to assess efficacy will be summarized using summary descriptive statistics by treatment group (combined placebo vs. 2 active treatment groups and combined placebo vs. combined treatment groups) and the total study population.

Linear mixed effect models will be used to estimate difference of changes from baseline between placebo and active treatment and to test whether there is dose-response for different outcomes. Generalized estimating equation (GEE) model will be used to estimate effects for the binary endpoints.

TABLE OF CONTENTS

STATISTICAL ANALYSIS PLAN	1
SIGNATURE PAGE	2
REVISIONS HISTORY LOG	2
SYNOPSIS.....	3
TABLE OF CONTENTS.....	6
LIST OF TABLES	8
1. LIST OF ABBREVIATIONS.....	9
2. INTRODUCTION	11
3. STUDY OBJECTIVES	12
3.1. Primary Objectives	12
3.2. Secondary Objectives	12
4. STUDY DESIGN	13
4.1. General Study Design and Plan	13
4.2. Study Population.....	13
4.2.1. Selection of Study Population.....	13
4.2.2. Subject Withdraw and Replacement.....	14
4.3. Randomization and Blinding.....	14
4.4. Study Assessments.....	14
4.4.1. Safety Assessment	19
4.4.2. Outcome Assessments	19
5. SAMPLE SIZE DETERMINATION	20
6. ANALYSIS POPULATIONS	21
7. GENERAL STATISTICAL CONSIDERATIONS.....	21
7.1. Interim Analyses and Data Monitoring	21
7.2. Multi-Center Studies.....	21
7.3. Multiple Comparisons / Multiplicity	21
7.4. Examination of Subgroups	21
7.5. Handling of Dropouts or Missing Data.....	21
7.6. Outlier Handling	21

7.7.	Adjustments for Covariates	21

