10.3. Vital Signs

Summary statistics (mean, standard deviation, median, min and max) of vital sign measurements and changes of measurements from predose for vital sign at each time point will be reported for pooled *hMaxi-K* and placebo in Table 14.3.4.3.

Individual vital sign records will be displayed in Listings 16.2.8.1 and 16.2.8.2.

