10.4. ECGs

Using the ECG overreader results, frequency and percentage of subjects in different degrees of QTcF categories (QTcF > 450, > 480 and > 500 msec) will be tabulated by treatment at each scheduled timepoint in Table 14.3.4.4. Summary statistics of ECG test parameters, ventricular heart rate (bpm), PR interval (ms), QRS duration (ms), QT/QTc (ms), P-R-T axes, average RR (ms), QTcB (ms), QTcF (ms), and change of these parameters from pre-dose to each post-dose timepoint will be calculated Table 14.3.4.5.1 for pooled *hMaxi-K* and placebo and Table 14.3.4.5.2 for 16,000 ug and 24,000 ug *hMaxi-K* group.

ECG overread overall assessment records will be displayed in Listing 16.2.8.3.1 and individual ECG site reading parameters will be listed in 16.2.8.3.2.

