13.1. General Reporting Conventions

All tables, figures and data listings will be presented in landscape orientation for easy visual comparison of different dose escalation cohorts. If figures presented, legends will be used for all figures with more than one variable or item displayed. Figure lines should be wide enough to see the line after being copied.

All titles will be centered on a page. The ICH numbering convention will be used for all TLFs. All tables, figures, and data listings will have the name of the relevant SAS (or Stata) program and a date-time stamp on the bottom of each output.

Number precision will be specified in the companion *ION-OAB Safety Table, Listing and Graphic Shells*.

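### SAP 10.2 and 10.3 name only pooled hMaxi-K and placebo for the laboratory and vital-sign tables, although the SAP synopsis promises safety summaries for each active dose group (minor)

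*SAP*

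**What the plan says.** The Statistical methods paragraph of the SAP synopsis covers safety and efficacy data in one sentence. It sets the grouping as "combined placebo vs. 2 active treatment groups and combined placebo vs. combined treatment groups", plus the total study population. That means two contrasts: placebo beside each dose, and placebo beside both doses together.

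Section 10 of the SAP then assigns the tables:

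- **Laboratory (10.2):** "Specifically, information of pooled *hMaxi-K* and placebo will be displayed in Table 14.3.4.1 for hematology and Table 14.3.4.2 for clinical chemistry".
- **Vital signs (10.3):** "vital sign at each time point will be reported for pooled *hMaxi-K* and placebo in Table 14.3.4.3".
- **ECG parameters (10.4):** "Table 14.3.4.5.1 for pooled *hMaxi-K* and placebo and Table 14.3.4.5.2 for 16,000 ug and 24,000 ug *hMaxi-K* group".
- **Adverse events (10.1):** tables by treatment group.

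Sections 10.2 and 10.3 also plan listings of individual records. Sections 13 and 16 leave table layout to a companion document of table, listing and graphic shells, which is not among the documents reviewed.

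**The concern.** The study gives two doses in sequence and its objectives put safety first. A reader of the report will want to see whether laboratory values or blood pressure moved more at 24,000 µg than at 16,000 µg. The synopsis says that comparison will be shown. The sections that allocate the tables do not provide it for haematology, chemistry or vital signs.

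A pooled column can hide a dose-related shift. If a mean change occurs at one dose only, averaging it with an unaffected group of the same size halves it.

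Small numbers do not explain the choice. SAP 9.1 plans by-dose efficacy contrasts on the same groups of six, including 24,000 µg against 16,000 µg with 95% confidence intervals.

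**Working it through.** The plan states no figure to reproduce on this point. The check compares the text first and then uses simple arithmetic.

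**1. Does pooled, in this SAP, include dose columns?** Section 10.4 uses the same pooled phrase for Table 14.3.4.5.1 and then names a separate Table 14.3.4.5.2 for the two doses. If the phrase already covered dose columns, the second table would be redundant. Sections 10.2 and 10.3 use the phrase and name no second table. The natural reading is that they plan no by-dose summary.

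**2. Group sizes** (SAP 3.2 and 4.1): active 6 + 6 = 12, placebo 3 + 3 = 6, total 18.

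**3. What pooling does to a shift at one dose.** This is an illustration. It assumes a within-group SD of 1, no shift in one dose group and a shift d in the other.

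- Pooled mean = (6×0 + 6×d)/12 = d/2.
- Pooled SD = √[(10×1 + 12×(d/2)²)/11].
- d = 1.0: mean 0.50, SD 1.09.
- d = 1.5: mean 0.75, SD 1.23.
- d = 2.0: mean 1.00, SD 1.41.

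**4. How precise would dose columns be?** The half-width of a 95% CI for a mean change, in SD units, is t(0.975, n−1)/√n.

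- n = 6: 2.571/2.449 = 1.05 SD.
- n = 12: 2.201/3.464 = 0.64 SD.

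**5. Injection number.** Protocol Table 6 and the kit label give 20 injections in Cohort 1 and 30 in Cohort 2. The label ties the number to the cohort, whether the vials hold drug or placebo.

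- Pooled active: 6 of 12 receive 30 injections, or 50%.
- Combined placebo: 3 of 6 receive 30 injections, or 50%.
- A 24,000 µg column: 6 of 6, or 100%, beside a combined placebo column at 50%.

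The pooled comparison is therefore balanced on procedure by design, and a by-dose column beside combined placebo is not. Both views have a use, so dose columns should be added without removing the pooled one.

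**The case against.** The best reply is that sections 10.2 and 10.3 do not exclude dose columns and that layout is delegated to shells not seen here. The shells may already contain them. This stands as a limit on certainty. The wording of 10.4 makes the pooled-only reading the more likely one, and if the shells do show doses, the text of 10.2 and 10.3 still needs to match them.

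A second reply is that little is lost. The protocol's Objectives make individual-level assessment of outliers primary, with descriptive statistics in support. Individual records are listed, and clinically significant laboratory abnormalities enter the adverse event tables, which are by treatment group. This also stands, and it keeps the point minor.

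Other passages might be read as further promises of by-dose tables, but they do not establish one:

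- The synopsis objective on laboratory tests, "changes and shift (whether the tests are within clinical normal range, whether they are clinically significant) from baseline by treatment", is met by active against placebo. The vital-signs item beside it does not mention treatment at all.
- SAP 13.1, "presented in landscape orientation for easy visual comparison of different dose escalation cohorts", is about page orientation.
- Protocol 10.4 ("will be analyzed using summary descriptive statistics for the two cohorts and the total study population") and the protocol synopsis ("will be analyzed using summary descriptive statistics for the four cohorts and the total study population") speak of cohorts and disagree on their number. A dose cohort holds six active and three placebo participants, so it is not a dose group.

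A reader might also infer that the pooled column is misleading because it mixes 20 and 30 injections. The allocation does not support that, since combined placebo has the same mix.

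**Conclusion.** The inconsistency is real and minor, held with moderate confidence. One sentence of the SAP synopsis promises safety summaries for each active dose, while sections 10.2 and 10.3 name only pooled hMaxi-K and placebo for three tables (14.3.4.1, 14.3.4.2 and 14.3.4.3). Section 10.4 shows that the SAP names a by-dose table where one is wanted.

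The consequence is limited to dose-level description in the report. A reader might go further and infer that dose-level safety data are lost or that escalation decisions are weakened. The documents do not support either inference. Listings keep the individual data, and SAP 7.1 says that no statistical analyses are performed for the DSMB reviews, so those reviews do not depend on these tables. No loss of power and no actual treatment effect is claimed.

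The conclusion assumes that the SAP text governs the output and that the planned numbers are reached (6 per dose, 6 placebo).

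**What to change.** In SAP 10.2 and 10.3, specify Tables 14.3.4.1 to 14.3.4.3 with four columns: combined placebo, 16,000 µg, 24,000 µg and pooled hMaxi-K. Keep the pooled column, because it is the one balanced with placebo on injection number. State that the dose columns are descriptive only, and bring the table shells into line. If pooling alone is intended, correct the grouping sentence in the Statistical methods paragraph of the synopsis instead.

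SAP section 2 requires the plan and any deviations to be final before the blind is broken, so the change belongs before that point. It affects text and shells only and needs no new data. The cost is longer tables whose dose columns have the limited precision calculated above.
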